STRYKER CONFIDENTIAL - THIS DOCUMENT CONTAINS CONFIDENTIAL AND PROPRIETARY INFORMATION THAT IS THE PROPERTY OF STRYKER CORPORATION. NEITHER THIS DOCUMENT NOR THE INFORMATION HEREIN MAY BE REPRODUCED, USED, OR DISCLOSED TO ANY THIRD PARTY WITHOUT THE PRIOR WRITTEN CONSENT OF STRYKER CORPORATION. CDM 10000023 Rev. AC

Trevo[®] Retriever Registry

Protocol Synopsis

Study Objective	
Primary Objective	To assess real world performance of the Trevo [®] Retriever which is intended to restore blood flow in the neurovasculature by removing thrombus in subjects experiencing ischemic stroke
Primary Endpoint	Revascularization status assessment at the end of the procedure using the modified TICI score
Secondary Endpoints	
 1. Day 90 mRS assessment 2. Day 90 all cause mortality 3. Neurological deterioration at 24 hours post procedure, defined as a four or more point increase in the NIHSS score from the baseline score 4. Rates of device and procedure related serious adverse events (AEs)
Other Key Assessments (Data points)	
 1. Time points will be collected on the following: stroke symptom onset, admission to initial hospital/emergency department, if transferred, time of arrival to second hospital, diagnostic imaging, start of Intravenous tissue Plasminogen Activator (IV tPA), angio suite arrival, arterial puncture, time of each Trevo pass, clot integration, Trevo removal and end of procedure (defined as the time of the final cerebral angiogram) 2. Data on the use of accessory products in conjunction with Trevo 3. Health economics, costs of hospitalization, length of stay, discharge disposition 4. Sub-study analysis of imaging (pre, angio, post) with an independent core lab measurement of ASPECTS, collaterals, modified TICI scores and core infarct volume. 5. Compare Day 90 outcome with pre-stroke mRS, baseline imaging and symptom onset to time of treatment.
Registry Device	Any approved Trevo Retriever approved for use by the local regulatory agency
Control	N/A
Device Sizes	All Trevo product sizes approved for use by the local regulatory agency
Study Design	
Study Design	Prospective, open-label, consecutive enrollment, multi-center, international registry
Planned Number of Subjects	Up to a maximum of 2000 subjects
Planned Number of Sites / Countries	Up to 100 sites worldwide
Efficacy Parameters	Post-procedural Modified TICI score
Follow-Up Schedule	
 a. Day 30 telephone contact b. Day 90 clinic visit
Key Inclusion Criteria	
 1. Subjects experiencing acute ischemic stroke who are eligible for restoration of blood flow using any approved Trevo Retriever in the neurovasculature to remove thrombus 2. Trevo Retriever is the initial mechanical neuro-thrombectomy device used to remove the thrombus

STRYKER CONFIDENTIAL - THIS DOCUMENT CONTAINS CONFIDENTIAL AND PROPRIETARY INFORMATION THAT IS THE PROPERTY OF STRYKER CORPORATION. NEITHER THIS DOCUMENT NOR THE INFORMATION HEREIN MAY BE REPRODUCED, USED, OR DISCLOSED TO ANY THIRD PARTY WITHOUT THE PRIOR WRITTEN CONSENT OF STRYKER CORPORATION.

CDM 1000023 Rev. AC

Trevo[®] Retriever Registry

	
3. Signed Informed Consent obtained4. Subject willing to comply with the protocol follow-up requirements5. Anticipated life expectancy of at least 3 months
Key Exclusion Criteria	The subject is participating in another mechanical neuro-thrombectomy device trial or any other clinical trial where the study procedure or treatment might confound the study end point.
Statistical Methods	
Statistical Test Method	
There will be no sample size/or power estimation for this single-arm registry.
 
Data analysis will be performed under guidance from the Study PIs, Steering Committee, and Sponsor.

Trevo[®] Retriever Registry

TABLE OF CONTENTS

1	Introduction and Rationale.....	9
2	Clinical Development Program for Trevo Retriever	9
2.1	TREVO Study.....	9
	Table 1. TREVO Study Primary and Secondary Endpoints ^[10]	10
	Table 2. TREVO Adjudicated Safety Events ^[10]	10
2.2	TREVO 2 Study.....	10
	Table 3. Primary Endpoint Results per the TREVO 2 (ITT population) ^[11]	11
	Table 4. Secondary Endpoints in TREVO 2 (ITT population) ^[11]	12
3	Study Device Description	12
	Figure 1a: Trevo Retrievers.....	13
	Figure 1b: Trevo Retrievers under fluoroscopy visualization.....	14
3.1	Device Labeling.....	15
4	Registry Objective.....	15
4.1	Primary Objective	15
5	Registry Endpoints.....	15
5.1	Primary Data point.....	15
5.2	Secondary Data points	15
5.3	Other Key Assessments (Data points)	15
6	Justification for the Registry Design	16
6.1	Method of Enrollment.....	16
7	Study Population.....	16
7.1	Selection Criteria	16
	7.1.1 Inclusion Criteria:	16
	7.1.2 Exclusion Criteria:	17

Trevo[®] Retriever Registry

1 Introduction and Rationale

Stroke is the fifth most common cause of death and the leading cause of adult disability in the United States. Each year stroke afflicts approximately 795,000 Americans causing over 130,000 deaths. Stroke costs the nation \$34 billion annually which includes the cost of medical care, medications and loss of productivity.^[1] Around the world approximately 15 million people each year will endure a stroke resulting in an estimated 5.5 million deaths. Of those patients who are alive at 90 days after their stroke, 50% have some type of disability with 26% dependent on others for daily living and 20% require institutional care. One in six people worldwide will experience a stroke in their lifetime.^[2-4] Good clinical outcomes in ischemic stroke have been shown to be strongly linked to revascularization.^[5]

Intravenous tissue plasminogen activator (IV tPA) is the only FDA approved therapy for acute ischemic stroke and must be given within three (3) hours of ischemic stroke symptom onset. Unfortunately, only a small percentage of stroke patients receive IV tPA therapy, with estimates ranging from 2.4% to 9%.^[6] Even so, the effect of IV tPA in patients in acute ischemic stroke has a short therapeutic time window^[7-8] and is limited by the large thrombus burden that occurs in the setting of proximal arterial occlusion. One study reported that IV tPA has nearly no potential to recanalize occluded vessels with a thrombus length exceeding 8 mm.^[9] When administered, IV tPA achieves early recanalization in only 30%–50% of subjects, with even lower recanalization rates in proximal large vessel occlusions (middle cerebral, basilar artery, and carotid terminus). Subjects who are ineligible for IV t-PA or who fail IV t-PA therapy are candidates for treatment with the Trevo Retriever. The Trevo Retriever received CE mark on December 18, 2009 and was cleared by the FDA on August 13, 2012 to restore blood flow in the neurovasculature by removing thrombus in patients experiencing ischemic stroke within 8 hours of symptom onset.

2 Clinical Development Program for Trevo Retriever

The principal goal in treating acute ischemic stroke is to restore cerebral blood flow as rapidly and safely as possible. Two clinical trials, the Thrombectomy REvascularization of large Vessel Oclusions (TREVO) in acute ischemic stroke and the TREVO 2 study, were conducted using the Trevo Retriever. Both clinical studies demonstrated that mechanical neurovascular thrombectomy can safely and effectively be performed up to eight (8) hours after onset of acute ischemic stroke symptoms.^[10-11]

2.1 TREVO Study

The TREVO study was a post marketing prospective, multi-center, single arm study performed at seven sites in Europe designed to quantify the performance of the Trevo Retriever in providing revascularization and clinical benefit to subjects experiencing a large vessel occlusion within 8 hours of symptom onset. The devices used in the study were the Trevo 4 x 20 mm, Trevo Pro 4, and Trevo 3 x 10 mm.

Sixty (60) subjects were enrolled between February 2010 and August 2011. Revascularization and intracranial hemorrhage at 24 hours were independently assessed by a central core lab. A Clinical Events Committee (CEC) independently reviewed all protocol-defined safety endpoints to determine relationship to the device and the procedure, and the causes of all deaths.

The primary endpoint in TREVO was defined as angiographic revascularization as measured by the independent core lab using the TICI scale. Success was defined as a final TICI score of 2a or better. Post procedure, successful revascularization was achieved in 91.7% of subjects. In the TREVO study, operators were not restricted from using intra-arterial (IA) lytic, but it was only used in 10% of cases.

Trevo[®] Retriever Registry

The secondary endpoints in TREVO were 90-day good clinical outcomes (defined as mRS of 0-2), 90 day mortality, device-related serious adverse events (DRSAEs) and symptomatic intracranial hemorrhage (SICH) at 24 hours (see **Table 1**).

Coincidentally, the rate of DRSAEs and SICH endpoints were both 5% (3/60), however the rates are not cumulative. One of the three SICHs was a DRSAE, while the other two were procedure-related. As mentioned above, one of the DRSAEs resulted in SICH while the other two DRSAEs were associated with subarachnoid hemorrhage (SAH).

Table 1. TREVO Study Primary and Secondary Endpoints ^[10]

Primary Effectiveness Endpoint	TREVO (N=60 subjects)
Revascularization	91.7% (55/60)
Secondary Endpoints	
90-Day Good Outcome (mRS = 0-2)	55.0% (33/60)
90-Day Mortality	20.0% (12/60)
Device-Related SAEs (DRSAEs)	5.0% (3/60)
SICH at 24 Hours (SITS-MOST)	5.0% (3/60)
SICH (ECASS III definition)	8.3% (5/60)

The TREVO protocol pre-defined specific events that were captured to assess safety which included vessel dissection, vessel perforations, ICH (as identified by core lab) and all deaths. Information for each of these events was collected and then independently adjudicated by the CEC. The results of this review are presented in **Table 2**. Most of the SAEs were attributed to the 12 deaths that occurred in the study, but a minority of the SAEs were related to the procedure (8.3%, 5 cases) or Trevo Retriever (5%, 3 cases).

Table 2. TREVO Adjudicated Safety Events ^[10]

Event	TREVO (N=60 subjects)
Serious Adverse Events (SAEs)	21.7% (13/60)
Procedure-Related SAEs	8.3% (5/60)
Device-Related SAEs	5.0% (3/60)

2.2 TREVO 2 Study

The TREVO 2 study was an IDE trial designed to support a 510k application for FDA clearance in the U.S. The trial^[8] enrolled 178 subjects between February 3, 2011 and December 1, 2011 at 26 sites in the United States and one site in Spain. The subjects were randomized 1:1 to Trevo (N=88) or Merci (N=90) and were stratified by age and baseline NIHSS to ensure balance in the two arms. The devices used in the study were the Trevo 4 x 20 mm in 10 subjects, and the Trevo Pro 4 in 78 subjects. The subjects treated with Merci[®] Retrievers were treated with commercially available product, at the discretion of the treating physician.

Trevo[®] Retriever Registry

The results for the primary effectiveness and safety endpoints are shown in the **Table 3**, and the results of the secondary endpoints are shown in **Table 4**.

Table 3. Primary Endpoint Results per the TREVO 2 (ITT population) ^[11]

Endpoint	Trevo (N=88)	Merci (N=90)	Difference [95% CI] ^a	p-value
Primary Effectiveness Endpoint:				
Post-Device Revascularization Success (TICI 2a+)*	86.4% (76/88)	60.0% (54/90)	26.4% [13.2%, 39.0%]	< 0.0001 ^b < 0.0001 ^c
Primary Safety Endpoint:				
Composite Events ***	14.8% (13/88)	23.3% (21/90)	-8.6% [-20.7%, 3.2%]	0.1826 ^d
Vessel Perforation	1.1% (1/88)	10.0% (9/90)	-8.9% [-17.0%, -2.2%]	
Intramural Arterial Dissection	0.0% (0/88)	1.1% (1/90)	-1.1% [-6.1%, 3.1%]	
Symptomatic ICH	6.8% (6/88)	8.9% (8/90)	-2.1% [-10.7%, 6.4%]	
Embolization to Previously Uninvolved Territory	6.8% (6/88)	4.4% (4/90)	2.4% [-5.0%, 10.3%]	
Access Site Complication Requiring Surgical Repair or Blood Transfusion	2.3% (2/88)	1.1% (1/90)	1.2% [-4.0%, 6.9%]	
Mortality within 24 hours	2.3% (2/88)**	0.0% (0/90)	2.3% [-1.9%, 7.9%]	
In vivo Device Failure	0.0% (0/88)	0.0% (0/90)	0.0% [-4.1%, 4.2%]	
Other PR-SAE	0.0% (0/88)	0.0% (0/90)	0.0% [-4.1%, 4.2%]	

* Administration of IA t-PA was counted as a failure for post-device revascularization.

** One death that occurred within 24 hours was related to the device, the other was attributed to the index stroke.

***Patients who experienced more than one safety event are counted only once in the composite safety endpoint.

a: By normal approximation; b: non-inferiority hypothesis using Blackwelder's method with non-inferiority margin of 10%; c: One-sided Wald test of superiority; d: Fisher's exact test.

STRYKER CONFIDENTIAL - THIS DOCUMENT CONTAINS CONFIDENTIAL AND PROPRIETARY INFORMATION THAT IS THE PROPERTY OF STRYKER CORPORATION. NEITHER THIS DOCUMENT NOR THE INFORMATION HEREIN MAY BE REPRODUCED, USED, OR DISCLOSED TO ANY THIRD PARTY WITHOUT THE PRIOR WRITTEN CONSENT OF STRYKER CORPORATION.

CDM 1000023 Rev. AC

Trevo[®] Retriever Registry

Table 4. Secondary Endpoints in TREVO 2 (ITT population) ^[11]

Endpoint	Trevo (N=88)	Merci (N=90)	Difference [95% CI] ^a	p-value
Time to Revascularization (mins) ^b Mean ± SD (N) Median (min, max)	47.8±44.2 (79) 34.0 (6.0, 209.0)	47.3±38.8 (81)40.0 (4.0, 207.0)	0.5 [11.4%] ^c	< 0.0001 ^d 0.5326 ^e
90-Day Good Outcome (Modified Rankin Score 0-2)	40.0% (34/85)	21.8% (19/87)	18.2% [4.2%, 31.7%]	0.0130 ^f
90-Day Mortality	33.0% (29/88)	23.6% (21/89)	9.4% [-4.2%, 22.7%]	0.1845 ^f
Asymptomatic ICH at 24 hours	40.9% (36/88)	53.3% (48/90)	-12.4% [-27.1%, 2.5%]	0.1017 ^f
Neurological Deterioration at 24 hours ^g	15.9% (14/88)	22.2% (20/90)	-6.3% [-18.4%, 5.5%]	0.3418 ^f

a: By normal approximation; b: Time to Revascularization was defined as the time from the start of the embolectomy procedure to achieving durable TIC1 2a or better or to the end of the procedure if TIC1 2a was not achieved. Subjects who had a baseline TIC1 score of 2a or did not have a study device used are excluded from this analysis (7 cases in Trevo arm, 8 cases in Merci arm); c: Per hypothesis testing setup, one-sided 95% upper confidence interval is used; d: One-sided Student's t-test of non-inferiority test with non-inferiority margin of 0.5 hours; e: One-sided Student's t-test of superiority test; f: Fisher's exact test; g: Defined as a four or more point increase in the NIHSS at 24 hours as compared to the baseline.

[figure not shown]
Overall the results of the TREVO and TREVO 2 trials demonstrate revascularization efficacy and safety of the Trevo Retriever.

3 Study Device Description

The Trevo Retriever is manufactured by Concentric Medical, a division of Stryker Neurovascular. The Trevo Retrievers consist of a self-expanding, laser cut, nitinol stent-like device permanently attached to a flexible, pusher wire. The retrievers have platinum markers at the distal end and platinum wires incorporated in the stent-like section to allow fluoroscopic visualization. (**Figure 1a and 1b**). The packaged Retriever is pre-loaded into the Insertion Tool. The device has a hydrophilic coating to reduce friction during use and a shaft marker to indicate proximity of the Trevo tip relative to Microcatheter tip.

Trevo[®] Retriever Registry

Figure 1a: Trevo Retrievers

STRYKER CONFIDENTIAL - THIS DOCUMENT CONTAINS CONFIDENTIAL AND PROPRIETARY INFORMATION THAT IS THE PROPERTY OF STRYKER CORPORATION. NEITHER THIS DOCUMENT NOR THE INFORMATION HEREIN MAY BE REPRODUCED, USED, OR DISCLOSED TO ANY THIRD PARTY WITHOUT THE PRIOR WRITTEN CONSENT OF STRYKER CORPORATION.

CDM 1000023 Rev. AC

Trevo[®] Retriever Registry

Figure 1b: Trevo Retrievers under fluoroscopy visualization

During the procedure, the Trevo ProVue Retriever is delivered to the thrombus using a microcatheter. The microcatheter is then retracted to deploy the shaped section of the Retriever. The shaped section engages and traps the clot. The Retriever and microcatheter are pulled back to dislodge the thrombus. The Retriever, the thrombus, and the microcatheter are then removed from the body.

The Trevo Retriever has been designed and tested to perform multiple retrieval attempts in a single subject. Per the Instructions for Use (IFU), each Trevo Retriever may be used for up to three (3) retrieval attempts. After each deployment of the device it should be thoroughly cleaned and inspected before reloading. No more than six (6) retrieval attempts should be performed in the same vessel using any combination of retrieval devices. Refer to the IFU for detailed instructions on how to use the device. The Trevo Retriever should not be re-sterilized and reused.

There are no specific contraindications for the use of the Trevo Retriever apart from the inclusion and exclusion criteria of this Investigational Plan. Refer to the IFU for a listing of warnings and precautions.

All Trevo Retriever models (e.g. Trevo[®] ProVue[™], Trevo[®] XP ProVue[™]) and device sizes will be allowed in the Trevo Registry upon receipt of local regulatory agency approval.

3.1 Device Labeling

A copy of the device Instructions for Use (IFU) is included in each device package. The Trevo labels and labeling contain the following information:

- Device Dimensions
- Lot Number
- Expiration (use before) date
- Microcatheter Compatibility

4 Registry Objective

4.1 Primary Objective

To assess real world performance of the FDA cleared/CE marked Trevo Retriever intended to restore blood flow in the neurovasculature by removing thrombus in patients experiencing ischemic stroke.

5 Registry Endpoints

Clinical data will be evaluated in all subjects where the Trevo Retriever is used as the initial thrombectomy device to remove thrombus from the neurovasculature in the setting of acute ischemic stroke.

5.1 Primary Data point

Revascularization status at the end of the procedure using the modified TIC1 score.

5.2 Secondary Data points

- a. Day 90 mRS (good clinical outcomes defined as mRS of 0-2)
- b. Day 90 mortality
- c. Neurological deterioration at 24 hours, defined as a four or more point increase in the NIHSS score from the baseline score
- d. Rates of device and procedure related serious AEs

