If adjunctive treatment (rescue therapy) is used AFTER the Trevo Retriever, biplane angiography should be performed immediately afterwards in order to reassess vessel patency and determine the effect of the adjunctive rescue treatment. The last angiogram prior to the use of rescue therapy will be considered when rating post-Trevo Retriever reperfusion.

NOTE: The Trevo thrombectomy procedure should be terminated if any of the following occur:

- Neurological deterioration or alteration in function is detected leading to the suspicion of an intracranial hemorrhage.
- Evidence of intracranial hemorrhage on imaging is noted.
- The occlusion is refractory to six retrieval attempts in a single vessel.

Neurological deterioration or alteration in function leading to the suspicion of an intracranial hemorrhage will necessitate an emergent head CT or MRI scan. At the discretion of the treating physician, this evaluation may also include angiography or other diagnostic tests to determine the etiology of the clinical alteration. Management of an intracranial hemorrhage will be performed according to each institution's usual practice.

8.4 24 hours (-6/+24) post procedure

The following data will be collected at 24 hours (-6/+24) post procedure:

- NIHSS (see **appendix G**)
- SAEs related to the device or procedure.
- For all subjects who expire prior to the 24 hours (-6/+24) assessment, available information regarding the primary cause of death and date/time of death will be recorded, as well as, whether the subject was made “do not resuscitate” (DNR) or “comfort care only” prior to expiration.

Any death or SAE must be reported to Stryker Neurovascular within 24 hours of becoming aware by eCRF completion.

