9.2 Analysis Populations

The Intent-to-treat principle will be followed to define the analysis population. All of the subjects who signed the informed consent and in whom Trevo Retriever was deployed through the microcatheter are considered enrolled and will be included in the analyses.

Sub-group analyses for the Registry will be performed under guidance from the Study PIs, Steering Committee, and Sponsor.

Day 90 outcomes will be compared to pre-stroke mRS status, baseline imaging and time of symptom onset to treatment. The first interim analysis will be performed after 300 subjects are enrolled and the results will be reported. Additional interim analyses and data reporting will occur throughout the study enrollment period.

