It is important that the Investigator and relevant study site personnel are available during monitoring visits and that sufficient time is devoted to the process. In order to perform her or his role well, the monitor must be given access to primary subject medical records which support the registry eCRFs. This access must be disclosed to the subject via the informed consent.

The investigator agrees to complete all registry requirements within three months of written notice of enrollment completion. Continuation of the registry beyond this time must be mutually agreed upon in writing by both the investigator and Stryker Neurovascular.

Stryker Neurovascular will conduct a registry closeout meeting with each Trevo Registry site after the final data query is generated and data requests are addressed. The purpose of the closeout meeting is to confirm that all registry-related activities are complete and site personnel are aware of the regulatory obligations following study closure activities. The closeout meeting may transpire remotely e.g. teleconference or at an on-site monitoring visit. The closeout activities include but are not limited to the following:

- Final regulatory document review and collection of any outstanding documents including a copy of the investigator notification letter sent to the IRB/EC regarding completion of the Trevo Retriever Registry
- Address and close any open action items
- Discuss record retention requirements
- Review publication guidelines

12 Auditing

Sites may be subject to a quality assurance audit by Stryker Neurovascular or its designees, or other regulatory authorities.

Trevo[®] Retriever Registry

It is important that the Investigator and relevant study personnel are available during any audits and that sufficient time is devoted to the process.

13 Device Accountability

There will be no device accountability or tracking as the Trevo Retriever has regulatory authorization to market the device.

14 Adverse Events

The following adverse events will be reported:

- all adverse events that occur during the procedure
- all SAEs related to the device or the procedure through Day 90
- all adverse events that result in death through Day 90

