Appendix B. Definitions

Adverse Event (AE):	Any unintended disease or injury or untoward clinical sign in a research subject. NOTE - This definition does not imply that there is a relationship between the adverse event and the device under investigation.
Device Malfunction/Nonconformity:	The failure of a device to meet its performance specifications or otherwise perform as intended. Performance specifications include all claims made in the labeling for the device. The intended performance of a device refers to the intended use for which the device is labeled or marketed.
Device-Related Serious Adverse Event (DRSAE):	Trevo device related vascular perforation or intramural arterial dissection, symptomatic ICH, embolization to a new territory, intra-procedural death, or device failure (in vivo breakage).
Distal Embolization (DE):	Any downstream occlusion distal to the target artery lesion, into the target ischemic territory, is considered DE unless complete angiogram or pre procedure non-invasive imaging demonstrated patency of these distal branches.
Embolization to New Territory:	Embolization into a previously uninvolved area of the brain, e.g. ACA embolization during MCA-M1 thrombectomy procedure.
Good Clinical Outcome:	A measure of neurologic functional outcome with a score of 0–2 on the modified Rankin Scale (mRS), usually assessed 90 days after treatment.
Irreversible Neurological Deterioration:	Neurological deterioration that is more than transitory, and is not related only to sedation. The neurological deterioration persists even after removal of sedation.
Modified Rankin Scale (mRS):	Scale for measuring the degree of disability or dependence in the daily activities of people who have suffered a stroke or other causes of neurological disability.
NIHSS Scale:	An assessment to objectively quantify the impairment caused by a stroke. It is composed of 11 items, each of which scores a specific ability between a 0 and 4. For each item, a score of 0 typically indicates normal function in that specific ability, while a higher score is indicative of some level of impairment. The individual scores from each item are summed in order to calculate a subject's total NIHSS score. The maximum possible score is 42, with the minimum score being a 0.
Pre-stroke disability:	Obtained at baseline, is representative of the subject's status before the index stroke, assessed by mRS on medical history obtained from subject, medical chart, or family members.

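### Neurological deterioration at 24 hours is defined by NIHSS rise alone, so a death before the 24-hour score is obtained is not an event and the rate is lower than one that counts early death

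*Protocol*

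**What the plan says.** The endpoint is defined twice in the protocol, in nearly the same terms. Section 5.2(c) has "Neurological deterioration at 24 hours, defined as a four or more point increase in the NIHSS score from the baseline score". The Synopsis has "Neurological deterioration at 24 hours post procedure, defined as a four or more point increase in the NIHSS score from the baseline score". Neither mentions death.

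Other parts of the protocol bear on how that definition works:

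- **Scale.** Appendix B says of the NIHSS: "The maximum possible score is 42, with the minimum score being a 0". It has no grade for death. The mRS in Appendix F does, at 6.
- **Timing.** Section 8.4 opens with "The following data will be collected at 24 hours (-6/+24) post procedure" and lists the NIHSS first. The window is therefore 18 to 48 hours after the procedure.
- **Early deaths.** Section 8.4 continues: "For all subjects who expire prior to the 24 hours (-6/+24) assessment, available information regarding the primary cause of death" is to be recorded, along with its date and time and any DNR or comfort-care status. Nothing links these deaths to the deterioration endpoint.
- **Population.** Section 9.2 says that consented subjects in whom the device was deployed "are considered enrolled and will be included in the analyses".
- **Neighbouring definition.** Appendix B defines symptomatic ICH with the same four-point NIHSS threshold, but adds death as an alternative way to qualify.

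**The concern.** Read as written, the definition needs a score at about 24 hours. A subject who dies before that score is taken cannot show a rise, so the worst possible early course does not count as deterioration. On this endpoint, dying before the assessment is scored more favourably than surviving with a four-point worsening.

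What is at stake is how one reported rate reads. Monitoring safety is among the registry's stated purposes (Section 6), and results are to be reported from the 300-subject interim onward (Section 9.2). A reader who sees a 24-hour deterioration rate may assume that it covers subjects who deteriorated to death within that time. No hypothesis test depends on it.

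**Working it through.** **Inputs**

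- TREVO 2, Trevo arm, deterioration at 24 hours: 14/88 (protocol Table 4; its footnote uses the same four-point NIHSS criterion).
- TREVO 2, Trevo arm, deaths within 24 hours: 2/88 (protocol Table 3). The footnote reads "One death that occurred within 24 hours was related to the device, the other was attributed to the index stroke".
- Registry maximum 2000 subjects; first interim at 300.
- The registry states no expected rate for this endpoint, so the TREVO 2 figures serve as assumptions. It is also assumed that neither TREVO 2 death had a 24-hour NIHSS.

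**Reproducing the stated figures.** 14/88 = 15.9% and 2/88 = 2.3%, as printed.

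**Direction.** Let x be survivors who meet the NIHSS criterion, d the early deaths without a score, and N all subjects.

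- Deaths kept as non-events: x/N < (x + d)/N whenever d > 0.
- Deaths dropped: x/(N − d) < (x + d)/N is equivalent to 0 < d(N − d − x), which holds whenever d > 0 and at least one survivor did not deteriorate.

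The rate is therefore lower than the death-inclusive rate under either denominator.

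**Size at the TREVO 2 figures.** The protocol does not say whether the two deaths are among the 14 events, so both cases are shown.

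| Case | Deaths as non-events | Deaths dropped | Deaths counted |
|---|---|---|---|
| Not among the 14 | 14/88 = 15.9% | 14/86 = 16.3% | 16/88 = 18.2% |
| Among the 14 | 12/88 = 13.6% | 12/86 = 14.0% | 14/88 = 15.9% |

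The shortfall is 2/88 = 2.27 points if deaths are kept. If they are dropped it is (2/88)(1 − 14/86) = 1.90 or (2/88)(1 − 12/86) = 1.96 points.

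**Sensitivity to the early-death share.** With p the early-death share and q the event rate among scored subjects (12/86 or 14/86), the shortfall is p if deaths are kept and p(1 − q) if dropped. The shares below other than 2.27% are illustrative and have no source in the protocol.

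| p | Kept | Dropped |
|---|---|---|
| 0.5% | 0.5 | 0.42 to 0.43 |
| 1% | 1.0 | 0.84 to 0.86 |
| 2.27% | 2.27 | 1.90 to 1.96 |
| 5% | 5.0 | 4.19 to 4.30 |

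The Clopper-Pearson 95% interval for 2/88 is 0.3% to 8.0%, so the data do not pin the share down.

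**Against sampling error.** The 95% half-width is 1.96 × √(0.159 × 0.841/N): 4.1 points at N = 300 and 1.6 points at N = 2000. A 2-point shortfall lies within sampling error at the interim and slightly exceeds it at full enrolment.

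**Survivors with no 24-hour score.** Let m be their share, and suppose that they deteriorate at the same rate q as scored subjects. Excluding them while keeping every death gives [p + q(1 − p − m)]/(1 − m). This exceeds p + q(1 − p) by pm(1 − q)/(1 − m). At p = 2/88 and an assumed m = 10% the excess is about 0.2 points.

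**The case against.** The strongest reply is that handling of deaths before a visit, and the denominator for each endpoint, belong in the SAP, which is not shown. An SAP could assign a worst NIHSS to these subjects or add death as an event. For the denominator this stands: its absence from Section 9.2 is no fault of the protocol. For the event it does not. The protocol fixes the event itself, twice; an SAP that followed it would carry the gap forward, and one that counted deaths would go beyond what the protocol states.

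A second reply is that keeping death apart from neurological deterioration is a legitimate choice, since death has its own endpoint in 5.2(b) and a composite would take in some non-neurological deaths. This is fair, and it is why the NIHSS-only rate and the causes of death should be reported alongside. But the protocol does not present the omission as a choice, and its own symptomatic ICH definition joins death to the same threshold.

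A third reply concerns size, and it largely stands. Two deaths are thin evidence. Deaths within 24 hours are not the same group as deaths before an assessment at 18 to 48 hours: a subject who dies after hour 18 may already have a score, while one whose assessment is late may die after hour 24 without one. Section 8.1 allows consent up to seven days after the procedure, so very early deaths may be under-represented unless a representative signs or a waiver applies.

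A reader might also infer that TREVO 2 under-counted deterioration. The documents do not show that. Table 4 uses all 88 subjects for this row but 85 for the mRS row, so the two early deaths were given some status, and which one is not stated.

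**Conclusion.** The point holds as a matter of definition: a subject who dies before a 24-hour NIHSS is obtained does not meet the endpoint as written, and the resulting rate is lower than one counting early death, whichever denominator is used. The shortfall is about 2 points if the TREVO 2 early-death share applies and those deaths had no score. It could be well below that.

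A reader might infer that early deaths vanish from the registry's results. They do not: they count in Day 90 mortality, as mRS 6, and, if judged related, in the serious adverse event rates of 5.2(d). Nor do the documents support treating the larger shortfalls in the sensitivity table as expected values. This is a worthwhile, inexpensive improvement to one descriptive secondary endpoint.

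**What to change.** In the Synopsis and in Section 5.2(c), define the event as a rise of at least four NIHSS points over baseline, or death before the 24-hour (-6/+24) NIHSS assessment. Report alongside it:

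- the NIHSS-only rate, for comparison with TREVO 2;
- the number and causes of the early deaths;
- the number of survivors with no 24-hour NIHSS.

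How those survivors are handled, and the denominator, can be left to the SAP, with a note that excluding them while keeping all deaths slightly over-weights deaths.

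The cost is one clause in two places and a few reported counts. No new data are needed: Section 8.4 already records cause and time of death, and Section 14 already requires reporting of "all adverse events that result in death through Day 90". The downside is a slightly less favourable rate that includes some non-neurological deaths, which the accompanying figures make visible.
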